## **DATA MANAGEMENT AND ANALYSIS**

**Outcomes:** This project will evaluate individual clinical outcomes, health care service utilization, client satisfaction, and implementation considerations; outcomes important to youth, family members, clinicians and policy-makers.

The *primary outcome measure* is change in Suicide Ideation Junior (SIQ-Jr) score. The SIQ-Jr is a youth-report measure of suicide risk behaviours that is valid, reliable, and sensitive to change and in accordance with youth preferences for self-administered mental health and SRB measures. The SIQ-Jr has 15 items, is reliable and valid in 12-18 year olds, and has been used in clinical trials, providing known effect sizes for sample size calculations.

*Secondary outcomes* include measures that are also feasible, reliable, valid and sensitive to change. These include:

(2a) Mental illness symptom severity, including those of depression, anxiety, substance use, psychosis, affective lability, and disruptive behaviour, as reported by youth and parents and measured by the Youth Self-Report, Life Problems Inventory, and Children's Behaviour Checklist); (2b) functional impairment, as assessed by the Columbia Impairment Screen (youth and parent report); (2c) family communication, assessed by the Conflict Behaviour Questionnaire (youth and parent report); (2d) cost-effectiveness analysis (CEA) of the incremental costs of the F-SPS as compared with UC in reducing SIQ-Jr score; and The frequency of ED and unscheduled (crisis) health appointments, using a health and social services diary and ICES databases, will be used to assess the effect of the F-SPS intervention on acute mental health crises. (2e) fidelity to the F-SPS intervention (implementation outcome) will employ a self-report measure to be developed by the project team. Measurement of treatment fidelity is key to understanding clinical and system level outcomes because an intervention cannot be effective unless it is appropriately implemented in the care pathway and developed with fidelity.

### **Power Analysis and Data Analytic Plan**

The sample size calculation is based on the assessment of between-group difference in change in SIQ-Jr score. This is a superiority study in which the implementation of the F-SPS intervention should only be recommended for study in a larger, multi-centre sample if the change in the primary outcome is significantly greater than in the control group. Two controlled clinical trials of an ED based intervention for suicidal youth have reported effect sizes of 0.4 for suicide attempt and 0.95 for suicidal ideation as measured by the SIQ-JR^23. A sample size of 128 participants provides 80% power ( $p=0.05$ ; 2-tailed t-test) to detect an effect size  $\geq 0.5$ , (based on a standard deviation [SD] of 14 and smallest clinically important difference of 7).

The principle of intent-to-treat will be applied to the analysis of outcomes. *H1*: The primary outcome SIQ-Jr will be compared between arms using repeated measures ANOCOVA with the corresponding baseline measure as the covariate. Mean differences and corresponding confidence intervals will be calculated. A two-sided, p-level of 0.05 will be applied for the primary outcome. *H2*: The number of unscheduled hospital visits will be compared between arms using a Poisson model. The two-sided level for the secondary outcomes will be adjusted (Bonferroni) to account for multiple testing. Implementation outcomes (i.e., fidelity to the intervention protocols) will inform client outcomes. Analysis of implementation data will be descriptive (fidelity to implementation of F-SPS model in both sites), and associative (statistical association of clinician fidelity to F-SPS and patient outcomes).

**Feasibility.** The ED at SickKids manages more adolescents with acute mental health presentations than any other hospital in the Toronto Central LHIN (TC-LHIN), on average 842 per year, (we estimate more than half for SRB). Sick Kids also has a strong history of successfully conducting ED-based RCTs and has

an established research infrastructure for identification and recruitment of potential research participants (Pediatric Research Academic Initiative at SickKids Emergency [PRAISE]). In addition, through our previous development work including an open pilot in the Urgent Care (Crisis) Clinic, several therapists at our centre are familiar with the intervention and have experience using it with acutely suicidal youth and families.

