In total there are four study visits. Participants will be assessed once by the study nurse at screening (the time of presentation in the ED), once by the study coordinator at baseline, and twice by the research assistant at 6 weeks post-randomization (at post-intervention), and 24 weeks post-randomization. Please see Table 1 for a complete measure administration schedule.

**Treatment allocation (F-SPS+UC or EUC):** Participants will be randomized to either receive the intervention, in addition to usual care (F-SPS+UC), or EUC only. They will be assigned in a 1:1 ratio of F-SPS+UC to EUC.

We will audio record F-SPS sessions if both the youth and the parent(s) or caregiver consent. These sessions will be reviewed by the principal investigators and the study staff in order to ensure fidelity to the treatment model.

In order to determine whether F-SPS+UC or EUC is related to a patient's health care service use, an analysis of participants' emergency room visits and unexpected medical appointments will also be conducted. OHIP numbers will be obtained at consent to link to ICES databases. .

We will recruit 128 adolescents to be randomized (64 adolescents per treatment arm) for this study (see 4.3 "Power Analysis").

**Intervention: F-SPS + UC (i)** is a manualized program that addresses the most common thoughts, feelings and conflicts that suicidal youth experience and teaches coping and safety skills to adolescents and their families. The program is the result of 3-years of development and quality improvement led by the PI ([name]), developed collaboratively with youth, families, and therapists. The program will be administered once weekly over 6 weeks by a trained therapist on an outpatient basis. Sessions consist of 1-hour spent one-to-one with the youth, followed by 1-hour with the youth and parent(s) or caregiver.

The therapist provides the youth and parent(s) or caregiver with a manual to use both during and between sessions. The program and manual address sources of conflict, ways to improve communication and ensure safety. The program resembles the only ED-based adolescent and family programs that have demonstrated effectiveness in decreasing suicidality. It is tailored to address the key concerns of the adolescent or family including mental health, academic problems, social or family conflict, acculturation issues, gender concerns or other stressors.

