#### **Measures:**

##### ***Primary Outcome Measures: Completed by Patient***

The **Suicide Ideation Questionnaire Junior High School Version (SIQ-Jr)** is a 15-item measure self-report of suicide ideation (e.g., thoughts about death and dying) completed by the patient. Items are scored from 0 to 6. The measure takes 5 minutes, and is completed in-person at baseline, week 6 and week 24.

The **Suicide Behavior Questionnaire – Revised (SBQ-R)** is a 4-item self-report questionnaire that measures suicide behaviour (i.e., previous suicide attempts or the likelihood of future attempts) over the

lifetime (at baseline) or over 1 month period (follow-up). The measure takes less than 5 minutes, and is completed in-person at baseline, week 6 and week 24.

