### **Participant Withdrawal Criteria**

Participants and/or parents or guardians have the right to withdraw from the study at any time for any reason. The investigator also has the right to withdraw participants from the study if it is in the best interest of the participant. Should a participant and/or parent or guardian decide to withdraw, efforts will be made to document the reason for the withdrawal, if provided.

Participant withdrawal criteria are as follows:

- Withdrawal of informed consent (participant's decision to withdraw for any reason)
- Serious adverse event which, in the opinion of the investigator, indicates that continued participation in the study is not in the best interest of the participant
- Participant or parent or guardian non-compliance

In the event a subject is withdrawn due to an AE, this will be documented and participants will continue to be followed until these events are resolved or stabilized, if possible.

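### The primary analysis is named as repeated measures ANCOVA, which in its classical form drops any youth missing one of the two follow-up SIQ-Jr scores; a likelihood mixed model should be named instead

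*Protocol*

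**What the plan says.** Under Power Analysis and Data Analytic Plan, the protocol states the principle, "The principle of intent-to-treat will be applied to the analysis of outcomes", and then the method for H1: "The primary outcome SIQ-Jr will be compared between arms using repeated measures ANOCOVA with the corresponding baseline measure as the covariate". It adds: "A two-sided, p-level of 0.05 will be applied for the primary outcome". It does not say how the model is fitted, or what happens to a youth who has one follow-up score but not the other.

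Under Primary Outcome Measures, the SIQ-Jr entry reads: "The measure takes 5 minutes, and is completed in-person at baseline, week 6 and week 24". So two post-randomisation scores, 18 weeks apart, enter the repeated measures. (Table 1 places the pre-randomisation score at screening; that does not affect this point.)

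Under Participant Withdrawal Criteria: "Participants and/or parents or guardians have the right to withdraw from the study at any time for any reason". Non-compliance by the participant, parent or guardian is also listed as a withdrawal criterion. Continued follow-up is mentioned only for withdrawal because of an adverse event.

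The sample size statement, "A sample size of 128 participants provides 80% power", is "based on a standard deviation [SD] of 14 and smallest clinically important difference of 7". The same 128 are to be randomised, 64 per arm, with no allowance for loss.

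**The concern.** Classical repeated measures ANCOVA works on one complete record per person. A youth assessed at week 6 but not at week 24 leaves the analysis, although a valid primary-outcome score exists. The analysis is then confined to completers, in tension with the intent-to-treat sentence directly before it.

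Two things are at stake. If loss is unrelated to outcome, precision is lost for no reason. If loss relates to the week-6 score differently in the two arms, the estimate is biased. Different loss is conceivable because the arms differ in contact: six weekly two-hour sessions in person for youth and family, against weekly telephone checks. The protocol makes this one test the condition for recommending a larger multi-centre study.

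**Working it through.** **1. The plan's own figure.** With 64 per arm, difference 7, SD 14 and a two-sided 0.05 t-test, the noncentrality is (7/14) × √(64/2) = 2.83 and the power is 80.1%. The stated 80% reproduces if all 128 are analysed. On that unadjusted basis, analysing only 90%, 80% or 70% of each arm gives 75.8%, 70.7% or 64.8%.

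**2. Inputs for the comparison of methods.** From the protocol: 64 per arm, SD 14, difference 7. Assumed: SD 14 and a true difference of 7 at both visits; correlations of 0.4 (baseline, week 6), 0.3 (baseline, week 24) and 0.6 (week 6, week 24); everyone seen at week 6; a fraction p also seen at week 24. The target is the between-arm difference averaged over the two visits, which is the arm effect in a repeated measures ANCOVA.

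**3. Random loss, by formula (large sample).** After adjustment for baseline:
- week-6 variance: 196 × (1 − 0.4²) = 164.64
- week-24 variance: 196 × (1 − 0.3²) = 178.36
- covariance: 196 × (0.6 − 0.4 × 0.3) = 94.08
- slope of week 24 on week 6: g = 94.08/164.64 = 0.571
- week-24 variance given week 6: 178.36 − 94.08²/164.64 = 124.60

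Completers only: variance = [(164.64 + 178.36 + 2 × 94.08)/4] × 2/(64p) = 4.150/p.

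Likelihood, all scores: variance = ¼ × [(1 + g)² × 164.64 × 2/64 + 124.60 × 2/(64p)] = ¼ × [12.705 + 3.894/p].

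| Lost after week 6 | Completers | All scores | Ratio |
|---|---|---|---|
| 0% | 4.150 | 4.150 | 1.00 |
| 10% | 4.611 | 4.258 | 1.08 |
| 20% | 5.187 | 4.393 | 1.18 |
| 30% | 5.928 | 4.567 | 1.30 |

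Simulation agrees: about 1.16 to 1.18 at 20%, and about 1.1 at 10%. Neither method is biased here.

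**4. Loss that depends on the week-6 score, by simulation.** Completers: regression of the two-visit mean on arm and baseline in youths with both scores. All scores: week-6 regression in everyone, then week 24 on week 6, arm and baseline in those observed, with the effects chained. The log-odds of loss change by 1 per SD of the week-6 score, with 20% lost per arm. The true reduction is 7.

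| Who is lost | Completers | All scores |
|---|---|---|
| EUC: higher scorers; F-SPS: random | 5.4 | 7.0 |
| EUC: lower scorers; F-SPS: random | 8.6 | 7.0 |
| F-SPS: higher scorers; EUC: random | 8.6 | 7.0 |
| Both arms: higher scorers | 7.0 | 7.0 |

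In the last row the completers' variance is about 6 to 12% larger across simulation runs. For the first row, 10% loss gives 6.2 and 30% loss gives 4.6; halving the log-odds to 0.5 at 20% loss gives 6.1. The all-scores column stays at 7.0 because the loss was generated as missing at random given week 6. It shows what the model corrects when that assumption holds, not that the assumption holds.

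**The case against.** The strongest reply is that the protocol never writes listwise deletion, a completers' set or a fitting method. Repeated measures ANCOVA is also used as a name for a likelihood model of the follow-up scores with baseline as covariate, and the intent-to-treat sentence points that way. This stands: a reader might infer that the plan prescribes a completers' analysis, and the text does not support that. Missing-data handling, covariance structure and degrees of freedom commonly belong in the SAP, which is not at hand, so their absence is not a fault. What remains is that the protocol does name a method, and the classical meaning of that name conflicts with the principle stated beside it.

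Second, no dropout rate or mechanism is given, and a right to withdraw is not a forecast of loss. This also stands. A reader might infer that the trial would be biased towards no effect; the table in the working shows that the sign depends on which youths leave which arm.

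Third, a reader might add that the method forces one common baseline slope on both visits. The text does not support this. The wide-format fit that deletes incomplete records gives each visit its own slope, so the two criticisms belong to different models.

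Fourth, a reader might take the t-test figures in step 1 as the power lost by the choice of method. They are not. Under the assumed correlations, baseline adjustment and averaging more than offset a 20% random loss: by normal approximation the completers' power is Φ(7/√5.187 − 1.96) = Φ(1.11), about 87%, against Φ(7/√4.393 − 1.96) = Φ(1.38), about 92%, with all scores.

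**Conclusion.** The point holds in a limited form. The named primary method can be read, in its classical sense, as excluding every youth with one missing follow-up score. That reading conflicts with the intent-to-treat statement, and the protocol does not exclude it. Under the assumed correlations, random loss of 20% costs about 16 to 18% in variance without bias, and 10% loss costs about 8 to 10%. Bias needs loss that depends on the week-6 score and does so differently by arm; with a strong dependence in one arm and 20% loss, the averaged effect could read about 5.4 or about 8.6 instead of 7. The loss rate, mechanism and correlations are all assumptions. The documents do not show that such bias will occur or in which direction. The case for acting is that the clarification costs almost nothing, whichever model the sponsor intended.

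**What to change.** Replace the H1 sentence, in the protocol or through the SAP, with: *SIQ-Jr at weeks 6 and 24 will be compared between arms with a likelihood-based mixed model for repeated measures (restricted maximum likelihood, unstructured within-person covariance, Kenward-Roger degrees of freedom) with arm, visit, arm-by-visit, baseline SIQ-Jr and baseline-by-visit, using every observed follow-up score of all randomised youth as randomised. The two-sided 0.05 test is applied to the between-arm difference averaged over weeks 6 and 24.*

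The contrast must be named because arm-by-visit yields several; the average is the arm effect that the planned analysis already tests.

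Cost: one sentence and no new data. With complete data the answer is practically unchanged (the two variances in the 0% row are equal). If a mixed model was always meant, this only makes it explicit.

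Limits: the model relies on data being missing at random and does not recover youths with no follow-up score. Add a sensitivity analysis that includes those youths and allows for departures from missing at random.

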## NARRATIVE SUMMARY

Suicide is the leading cause of death due to illness among Canadian youth, claiming more lives than any medical illness, including cancer. Suicide prevention is possible, and early intervention is urgently needed. Consistent with previous research highlighting the need for emergency department (ED) based suicide prevention strategies we previously showed that youth who present to the ED seeking help for suicide-related behaviours are at particularly high risk of eventual suicide after discharge. The standard of care for youth presenting with suicidal ideation and risk behaviour (SRB) to the ED is that the ED personnel places a referral to a community mental health agency (CMHA), or refers the patient back to their usual health care provider for ongoing care. This represents usual care (UC). It is common for the standard of care that (i) immediate service does not occur, as patients are often placed on wait lists; (ii) families are expected to make the CMHA contact there is often no follow through; (iii) the treatment provided does not include crisis management; and (iv) many youth are connected to therapists inexperienced with crises, all of which result in further ED re-visits for suicidal behaviour.

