### **Hypothesis**

1. To determine the effect of a Focused Suicide Prevention Strategy added to usual care (F-SPS + UC) on SRB. Hypothesis 1 (H1): Compared with EUC, we hypothesize that the F-SPS + UC will be effective in decreasing SRBs over the 6-month follow up period.
2. To examine the effect of F-SPS + UC on future acute mental health crises (ED and unscheduled health care visits). Hypothesis 2 (H2): Compared with EUC, we hypothesize that participants who

receive the F-SPS + UC intervention will have significantly fewer acute mental health crises.

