Participants will also have access to the UC recommended by the ED circle of care. The F-SPS program will not interfere with the youth's ongoing plan of care. The F-SPS therapist will communicate with the youth's UC provider following the completion of the intervention, and provide detailed information about the intervention to the UC provider. This communication ensures that the UC provider is also informed about the challenges and strategies for the participant, so that the UC therapist is better able to assist the participant should similar situations reoccur in the future.

**Comparator: Enhanced Usual Care.** The comparator arm consists of weekly telephone checks for six weeks following the ED visit in addition to the UC recommended by the ED circle of care. The study coordinator will also contact parents in the comparator arm by telephone once weekly for six weeks. They will review changes to the youth's usual care and their contact with community resources in the 7 days prior to the phone call. As such, the aim of the EUC comparator is to improve access to mental health resources. It is not a therapeutic intervention in and of itself. The study coordinator will provide further information regarding community mental health resources as needed. If the parent indicates that the youth is in immediate risk for suicidal behaviour, 911 will be called. The ED team's referral suggestions plus weekly telephone follow-up represents EUC.

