***Secondary Outcome Measures: Completed by Parent(s) or Caregiver***

The **Child Behavior Checklist (CBCL)** is a 112-item measure, completed by a parent or caregiver, of a child's behavioral, emotional and social problems over a 6 month period at baseline, and a 2 week period at follow-up. There are eight subscales: anxious/depressed, withdrawn/depressed, somatic complaints, social problems, thought problems, attention problems, rule-breaking behavior, and aggressive behavior. The measure takes 30 minutes, and is completed through REDCap at baseline, week 6 and week 24.

The **Children's Affective Lability Scale (CALS)** is a 20 item parent-report instrument that measures difficulties with emotion regulation on 5 point Likert scale. The measure takes five minutes, and is completed through REDcap at baseline, week 6 and week 24.

The **Columbia Impairment Scale – Parent Report (CIS-PR)** is a 13 item scale designed to measure functioning on a 5 point Likert scale. This measure is completed by both the child/adolescent and the parent(s). The measure takes 5 minutes and is completed through REDcap at baseline, week 6 and week 24.

The **Conflict Behavior Questionnaire– Parent Report (CBQ-PR)** is a 20 item scale that has a youth report and parent report version that examines the parent-child relationship and measures conflict over a 6 month period at baseline, and over a 2 week period at follow-up. The measure takes 5 minutes, and is completed through REDcap at baseline, week 6 and week 24.

The basic **demographic information** is collected at the initial assessment. This will include age, sex, date of birth, education, household income, parent occupation, and ethnicity. The measure takes five minutes, and is completed through REDcap at baseline.

The **Evaluation Form: Parent Version** is an 8-item, mixed quantitative and qualitative measure designed for this study that solicits feedback from parents of children enrolled either the F-SPS + UC arm or the ECU arm. This measure takes 5 minutes, and is completed through REDCap at week 6.

The **Health Care Utilization Survey (HCUS)** is a self-report questionnaire of participants' use of available health care services, medication, and the costs associated with those services. There are 11 questions that a participant answers, with an additional follow-up questions depending on answers. It takes 15 minutes, and is completed by the parent(s) or caregiver through REDCap at baseline and 24-weeks.

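### The H2 analysis sentence names unscheduled hospital visits, narrower than the outcome H2 defines; it also names a plain Poisson model, and the protocol contradicts itself on H2's alpha level

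*Protocol*

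**What the plan says.** The Hypothesis section sets the aim of H2: "To examine the effect of F-SPS + UC on future acute mental health crises (ED and unscheduled health care visits". The Procedure section describes the matching analysis of service use: "emergency room visits and unexpected medical appointments will also be conducted". The outcome list under Data Management and Analysis gives the same scope and its sources: "The frequency of ED and unscheduled (crisis) health appointments, using a health and social services diary and ICES databases".

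Under Power Analysis and Data Analytic Plan, the sentence labelled H2 reads: "The number of unscheduled hospital visits will be compared between arms using a Poisson model". It is the only sentence that says what is modelled. The next sentence applies a Bonferroni adjustment to the secondary outcomes, without giving the number of tests. A two-sided 0.05 is kept for the primary outcome.

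The status of H2 is stated in two ways. The Narrative Summary puts mental health crises among the primary outcomes. Data Management and Analysis names change in SIQ-Jr as the primary outcome and places the visit count among the secondary ones.

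**The concern.** There are three defects, all confined to H2.

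- **Scope.** An analyst who follows the analysis sentence literally would leave out events that H2 counts, namely unscheduled visits outside a hospital. With two candidate counts for one hypothesis, the choice could also be made after the data are seen.
- **Variance.** The default Poisson variance equals the mean. If participants differ in their underlying visit rate, the standard error is too small and a difference is declared too often. A Bonferroni adjustment lowers the threshold but does not repair the standard error.
- **Alpha level.** If crises are primary, H2 would be tested at 0.05; if secondary, at the adjusted level. The protocol supports both readings.

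H2 predicts significantly fewer acute crises, so the count, the standard error and the threshold all bear on whether that claim can be made.

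**Working it through.** **Figure stated in the plan.** The protocol gives no visit rate, dispersion or power for H2, so no H2 figure can be reproduced. Its one sample size, for the SIQ-Jr, holds. With SD 14 and difference 7, n per arm = 2 × (1.96 + 0.842)² × (14/7)² = 62.8, so 63 per arm and 126 in total, against 128 stated. Power at 64 per arm is 0.801 by the noncentral t.

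**Step 1: the count.** Set side by side:
- Hypothesis: ED visits and unscheduled health care visits.
- Procedure: emergency room visits and unexpected medical appointments.
- Outcome list: ED and unscheduled (crisis) health appointments.
- Analysis sentence: unscheduled hospital visits.

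The first three agree. ED visits fall within the fourth on any reading; unscheduled visits outside a hospital do not.

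**Step 2: what a narrower count would cost.** All inputs here are assumptions except 64 per arm: EUC mean 1.0 visits on the H2 definition, rate ratio 0.6, gamma-distributed rates with shape k, and the same hospital share s in both arms. The variance of the log rate ratio is approximately (1/64) × [1/(1.0s) + 1/(0.6s) + 2/k].
- For k = 1 and s = 1: (1 + 1.667 + 2)/64 = 0.0729, SE 0.270. Then |ln 0.6|/SE = 0.511/0.270 = 1.89, and power at 5% is Φ(1.89 − 1.96) = 47%.
- For k = 1 and s = 0.6: (1.667 + 2.778 + 2)/64 = 0.1007, SE 0.317, ratio 1.61, power Φ(−0.35) = 36%.

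Simulation with Pearson-scaled standard errors agrees closely. Power for s = 100/80/60/40%:

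| Test level | k | Power |
|---|---|---|
| 0.05 | 2 | 56/49/41/30% |
| 0.05 | 1 | 46/41/35/27% |
| 0.05 | 0.5 | 34/31/27/23% |
| 0.0056 | 1 | about 16/13/10/6% |

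The level 0.0056 is 0.05/9. Nine tests is an assumption, because the number is not stated.

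**Step 3: the Poisson variance.** Let φ be the variance-to-mean ratio; for gamma-Poisson counts φ = 1 + mean/k. The approximate type I error of an unscaled two-sided test at level α is 2 × [1 − Φ(z/√φ)], where z is the usual critical value.
- α = 0.05, z = 1.96: 5.0% at φ = 1, 11.0% at 1.5, 16.6% at 2, 25.8% at 3.
- α = 0.0056, z = 2.77: 0.6% at φ = 1, 2.4% at 1.5, 5.0% at 2, 10.9% at 3.

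Simulation at 64 per arm, with means of 0.3 to 1.0 visits and k = 2, 1 or 0.5 (φ from 1.15 to 3), gives 6.2% to about 25% at 0.05 and about 0.7% to 10% at 0.0056. With truly Poisson counts the error at 0.05 is 4.5% to 4.9%. Pearson scaling with a t reference on 126 degrees of freedom gives about 4.6% to 5.1% at 0.05 and 0.3% to 0.5% at 0.0056 in the overdispersed cases.

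**Step 4: the alpha level.** The Narrative Summary makes crises primary; Data Management and Analysis makes them secondary. With nine tests assumed, the two readings put the threshold at 0.05 or at 0.0056.

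**The case against.** **Shorthand.** The analysis sentence carries the H2 label, and three sections define H2 alike, so loose wording is the likelier explanation. That is fair. A reader might infer that the trial intends to count hospital visits and nothing else, but the sentence contains no such restriction and nothing else in the protocol supports it. What stands is that the one sentence fixing the modelled count does not match the outcome.

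**Variance left to the analysis plan.** The protocol names a Poisson model without saying how its variance is estimated, and a statistical analysis plan, not shown, may already scale it. That also stands in part. A reader might infer that the H2 test is invalid. The documents do not show this, because they give no visit rate or dispersion. Mixed presentations (ideation through attempt) and uneven usual care, for example "immediate service does not occur, as patients are often placed on wait lists", make varying rates plausible and no more. The point survives as an inexpensive improvement to a named model whose default is restrictive.

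**Place of care differing by arm.** The protocol says "the aim of the EUC comparator is to improve access to mental health resources". A reader might infer that the comparator moves crisis visits out of hospital, so that a hospital count would be biased between arms. The documents do not support this. They do not say that unscheduled visits shift location, and the intervention arm also has access to usual care. Any pair of arm-specific hospital shares would be invented, so none is used here.

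**Conclusion.** The concern holds as a minor one. The mismatch in the count and the conflict over whether crises are primary or secondary are both in the text and need no assumption. The size of the effect does rest on assumptions. In the k = 1 case, a hospital share of 40% to 80% lowers power from 46% to between 27% and 41% at 5%, or from about 16% to between 6% and 13% at 0.0056. If nearly all unscheduled visits are hospital visits, the loss is negligible.

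The Poisson inflation likewise runs from none to large, and the documents do not say where this trial lies. The consequences stop at H2. The SIQ-Jr analysis, the 128 participants and the rule for recommending a larger study do not depend on it.

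**What to change.** In Power Analysis and Data Analytic Plan, reword the H2 sentence to say that the number of ED and unscheduled health care visits, as defined in H2, will be compared between arms using a Poisson model with Pearson-scaled standard errors, or negative binomial regression. In the Narrative Summary, list mental health crises as a secondary outcome, so that H2 is tested at the Bonferroni-adjusted level.

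**Cost in precision.** H2 intervals widen if counts are overdispersed: about 8% at a variance-to-mean ratio of 1.15, 23% at 1.5, 41% at 2 and 71% at 3. If counts are truly Poisson they widen by 0.8%, and power falls by at most 1.1 points (0.416 to 0.405 in the worse of two cases simulated).

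**Cost in measurement.** The wider count may take in less acute contacts. Its sources also need settling. Linkage is planned ("OHIP numbers will be obtained at consent to link to ICES databases"), and a parent-completed survey covers "use of available health care services, medication, and the costs associated with those services" at baseline and week 24. However, the diary named in the outcome list appears neither under Measures nor in Table 1. Where the count rests on reports by unblinded parents rather than on ICES data, it is open to reporting differences between arms. The revised text should therefore say which source defines the count.

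### The H2 visit-count model names no baseline covariate; prior visits from the planned ICES linkage, with an overdispersion-tolerant variance, would be a cheap optional gain in precision

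*Protocol*

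**What the plan says.** The Hypothesis section gives two hypotheses. H2 is that participants who "receive the F-SPS + UC intervention will have significantly fewer acute mental health crises".

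The Power Analysis and Data Analytic Plan treats the two in turn. H1 is analysed by "repeated measures ANOCOVA with the corresponding baseline measure as the covariate". H2 follows: "The number of unscheduled hospital visits will be compared between arms using a Poisson model". No covariate and no treatment of overdispersion is named for H2. On error control it adds: "The two-sided level for the secondary outcomes will be adjusted (Bonferroni) to account for multiple testing". The number of tests is not given.

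Two sources could supply prior service use:

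- **ICES.** Under Procedure, "OHIP numbers will be obtained at consent to link to ICES databases". Data Management and Analysis says of the crisis-visit count: "using a health and social services diary and ICES databases, will be used to assess the effect of the F-SPS intervention on acute mental health". The stated purpose is outcome ascertainment; no period before randomisation is mentioned.
- **HCUS.** This "is a self-report questionnaire of participants' use of available health care services, medication, and the costs associated with those services", and it "is completed by the parent(s) or caregiver through REDCap at baseline and 24-weeks"; Table 1 agrees. No recall period is given.

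**The concern.** Youths may differ widely in how often they use emergency services. If so, part of the variation in follow-up visits is predictable from earlier visits, and a model with arm alone leaves it in the error. With 64 per arm and no stratification named, chance imbalance in a few frequent attenders could also move the rate ratio.

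Power for H2 is not assured. The sample size was set for SIQ-Jr only, and H2 faces a reduced significance level if it falls under the secondary-outcome rule. A covariate that costs almost nothing is therefore worth considering. The look-back matters for timing: a later analysis plan can adjust only for data that were extracted.

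**Working it through.** **1. The plan's own figure.** SD 14, difference 7, two-sided 0.05 and 80% power give 63.77 per arm by the exact t-test, so 64 per arm and 128 in total, with power 0.801. The stated figure reproduces, but it concerns SIQ-Jr. No figure is stated for H2.

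**2. Formula for H2.** With n = 64 per arm, arm means μ₀ and μ₁, between-patient overdispersion k, and R² the share of it explained by prior use:

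Var(log RR) = [1/μ₀ + 1/μ₁ + 2k(1 − R²)] / 64

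Everything except n is assumed; μ₁ = 0.6 μ₀ throughout. Power = Φ(|ln 0.6|/SE − 1.96), with |ln 0.6| = 0.511.

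- Central case (μ₀ = 1, k = 1, R² = 0.25). Unadjusted: (1 + 1.667 + 2)/64 = 0.0729, SE 0.270, power 47%. Adjusted: (1 + 1.667 + 1.5)/64 = 0.0651, SE 0.255, power 52%. The variance falls by 0.5/4.667 = 10.7%.
- Low case (0.3, 0.5, 0.1). The bracket goes from 9.889 to 9.789, a 1% fall; power 25.4% to 25.7%.
- High case (2, 2, 0.5). The bracket goes from 5.333 to 3.333, a 37.5% fall; power 42% to 61%.

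**3. Bonferroni level.** As an illustration only, five tests (the number of lettered secondary objectives) give 0.05/5 = 0.01 and a critical value of 2.576. Central case: Φ(0.511/0.270 − 2.576) = 25% unadjusted and Φ(0.511/0.255 − 2.576) = 28% adjusted.

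**4. Simulation** (1,000 runs per setting, 64 per arm, log-normal heterogeneity with log-scale variance 0.7, covariate log(prior count + 0.5), rate ratio 0.6). A log-scale correlation ρ corresponds in the control arm to a count correlation of μ²(e^(0.7ρ) − 1) / [μ + μ²(e^0.7 − 1)].

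| Control mean | ρ | Count correlation | Fall in true variance |
|---|---|---|---|
| 0.5 | 0.3 / 0.6 / 0.9 | 0.08 / 0.17 / 0.29 | 0% / 1% / 5% |
| 1.0 | 0.3 / 0.6 / 0.9 | 0.12 / 0.26 / 0.44 | 1% / 6% / 16% |
| 2.0 | 0.3 / 0.6 / 0.9 | 0.15 / 0.35 / 0.58 | 1% / 10% / 27% |

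A second simulation (1,500 runs, mean 1, dispersion-corrected Poisson, covariate log(1 + prior count)) gave unadjusted-to-adjusted variance ratios of 0.99, 1.03, 1.13 and 1.20 at count correlations of 0.11, 0.25, 0.35 and 0.43. The last two are falls of 1 − 1/1.13 = 12% and 1 − 1/1.20 = 17%. Power rose from 48% to 52% and from 37% to 47%. The two starting values differ, so dispersion changed along with the correlation; the gains should not be read as effects of correlation alone.

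**5. What a plain Poisson model would report.** At mean 1.0 its standard error went from 0.208 to 0.209 on adjustment, because it depends on event counts alone. The true sampling SD at ρ = 0.9 went from 0.280 to 0.257, and the robust standard error tracked it (0.266 to 0.245). With heterogeneity (ρ = 0.6) and no true effect, the plain Poisson test rejected in 11.5% to 24% of runs at nominal 5%. Adjustment brought this only to 10.5% to 22%. A robust standard error gave about 5% to 7%.

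**The case against.** The strongest objection is that the protocol is silent, not wrong. A reader might infer from the contrast with H1 that H2 is fixed as an unadjusted comparison. The text does not say so: a Poisson model is a regression that can carry covariates, and covariates for such a model are commonly left to an analysis plan, which is not at hand. This stands, and it is why the point is a suggestion.

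A reader might also infer that the trial already holds each youth's visit history. The documents support only the means of obtaining it. Linkage would permit a look-back, but none is described, and the HCUS recall period is not given.

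Nor would the covariate by itself narrow the reported interval. Under the plain Poisson model it does not (step 5), so the benefit depends on also changing the variance. That second change matters more for the validity of H2 than the covariate does for its precision.

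Finally, the HCUS is a doubtful stand-in. Procedure has the coordinator book the baseline visit by telephone and then randomise, without saying that baseline measures come first, and families are not blinded. A parent could report prior use after learning the allocation. This also stands and limits the fix.

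The objection does not remove the core: H2 names no covariate, a suitable one is within reach of a linkage already planned, and visits before the index presentation cannot be affected by allocation.

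**Conclusion.** The point holds as an optional gain in precision. On assumed control means of 0.5 to 2 visits and a rate ratio of 0.6, the gain is essentially nil at weak correlation between earlier and later counts and roughly 10% to 20% of the variance at 0.35 to 0.45. The matching gain in power is a few to about 10 percentage points at two-sided 0.05. More extreme assumptions give more (37.5% in the high formula case). With no between-patient heterogeneity there is no gain. None of the visit rates, dispersion or correlations comes from the documents.

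The direction is well supported; the size is not. The documents do not support reading this as a contradiction, or as a demonstrated loss of power.

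**What to change.** State that the H2 model includes arm and log(1 + number of the same type of visits in the 12 months before the index ED visit, from ICES), fitted with a dispersion-corrected or robust variance. Add the 12-month look-back to the ICES extraction. Settle both before outcome data are seen by arm.

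Do not fill in the HCUS count person by person where ICES history is missing; that would mix a parent report of unstated recall with administrative counts. If ICES history is unavailable for the whole trial, use the HCUS count for everyone, and only where it was completed before randomisation.

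The cost is one model covariate, a choice of variance estimator and one line in the data request. No new contact with families is needed.
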